12.6 Statistical Hypothesis

The study aims are to explore, compare and describe the data for research purposes; no hypotheses are pre-specified.

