12.7 Analysis of Primary Variable

The primary variables are the pharmacokinetic properties:

- Area under the curve (microg/ml x h): ≥ 5
- Cmax: $\geq 0,8$
- Tmax: ≥ 3
- elimination half-life (t 1/2)

At each time point and for each group, descriptive statistics and 90% confidence intervals will be provided. See section **12.1** for details.

Analysis of primary endpoints will be performed on Intention-To-Treat population and Per Protocol population.

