4.8 Multiple testing

Not applicable in this study.

	Form	Form No.	1M-DMST-011-01-A1
	Statistical Analysis Plan	Page	Page 13 of 69
		Effective Date	07/05/2018

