5.2 Efficacy Analysis

5.2.1 Primary Efficacy Analysis

The primary objective of this study is to evaluate the best dosage between 100mg once daily or 100mg twice daily for COQUN ORAL FORMULATION in order to reach a level of plasma concentration which might assure its antioxidant effect if taken on a regular basis.

The following pharmacokinetic properties will be evaluated:

- Area under the curve (microg/ml x h)
- C_{max}
- T_{max}
- Elimination half-life (t_{1/2})

Collected Variables

- Plasma concentration of coenzyme Q10 [CRF – Visit 2, 3, 4, 5]

	Form	Form No.	1M-DMST-011-01-A1
	Statistical Analysis Plan	Page	Page 21 of 69
		Effective Date	07/05/2018

Derived Variables

Derived variables are shown in Image 1 and are the following^[2,3]:

- AUC_t
The area under the plasma concentration curve to the last quantifiable concentration (C_t) at time t (AUC_t) will be determined by linear trapezoidal rule. The trapezoidal rule is a method used to numerically approximate the area under the concentration by time curve obtained by summing the area of all trapezoids constructed under the curve. Each trapezoid's area is obtained as:

$$\frac{(C_i + C_{i+1}) * (T_{i+1} - T_i)}{2}$$

where C_i is the concentration at time i (where i is any timepoint before the last observed timepoint T_t), C_{i+1} is the concentration at the following timepoint, T_i is the timepoint i and T_{i+1} is the following timepoint.

- C_{max}
Maximum concentration in the plasma (C_{max}) is obtained directly from the data being the highest plasma concentration value.
- T_{max}
 T_{max} is the collection time in which the maximum concentration is observed and is related to the drug absorption speed.
- $t_{\frac{1}{2}}$
The terminal half-life is defined as the time required for the plasma concentration of a drug to decrease 50% in the final stage of its elimination; this parameter is computed with the formula^[2]:

$$t_{\frac{1}{2}} = \frac{\ln 2}{\lambda_z}$$

where λ_z is the smallest elimination rate constant observed which is obtained as the ratio of clearance and volume of distribution. Clearance is calculated as the ratio of dose and AUC while volume of distribution is obtained as dose divided by concentration at time 0 that is the concentration registered after the first intake of coenzyme (in the single dose time 0 is hour 1, in the multidose phase time 0 is visit 2).

[figure not shown]

Image 1. Pharmacokinetic parameters

	Form	Form No.	1M-DMST-011-01-A1

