	Statistical Analysis Plan	Page	Page 22 of 69
		Effective Date	07/05/2018

Analysis of Primary Efficacy variable:

Descriptive statistics such as mean \pm standard deviation, median with interquartile range, minimum, maximum and coefficient of variation will be presented for the plasma concentration of coenzyme Q10 at each time point in the entire sample of subjects. 95% confidence interval will be provided as well.

An explorative analysis on gender will be performed showing descriptive statistics for plasma concentration of coenzyme Q10 by gender. The effect of gender will be explored by means of a mixed model for repeated measures with covariates *gender*, time and the interaction term *gender*time*.

Descriptive statistics will be also provided for the plasma concentration of coenzyme Q10 at each time point by treatment group.

Change of plasma concentration versus baseline (i.e. change versus visit 2 values) will be computed for each study visit both for the whole sample and by treatment group.

Change will be computed in the following way:

$$\text{Change (\%)} = \frac{\text{Value at Visit X} - \text{Baseline Value}}{\text{Baseline Value}} \times 100$$

Area under the curve, maximum concentration in the plasma, time of maximum concentration and terminal half-life will be presented descriptively on the original scale.

95% confidence interval will be provided for the means of 100mg OD and 100mg BID for COQUN ORAL FORMULATION for the parameters AUC_t , C_{max} , T_{max} and terminal half-life. A Student t-test for unpaired data will be performed in order to detect differences between the two groups in the pharmacokinetics parameters.

A concentration by time graph will be presented for the multidose phase by treatment group in order to have a graphical visualization of the pharmacokinetics properties over time.

Line graphs will be provided for the concentration of coenzyme Q10 in the whole sample and by gender.

In performing statistical analysis, it is important to assess the statistical outliers. In fact, inclusion or exclusion of outlying subjects may lead to a different conclusion in assessment of differences in bioavailability between two formulations. It is therefore important to identify these outliers and study their effects.

Primary endpoint will be evaluated on the ITT population and analysis will be replied on the PP population. Results obtained on the PP population will be considered as supportive of those obtained on the ITT set.

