Imputations for missing values: No imputation of missing data will be performed

Analysis Sets to be used for:	Tables	ITT and PP analysis set
	Listings	ITT analysis set
	Figures	ITT and PP analysis set

	Form	Form No.	1M-DMST-011-01-A1
	Statistical Analysis Plan	Page	Page 23 of 69
		Effective Date	07/05/2018

Primary efficacy variable will be summarized by treatment group as follows:

Table 13. Primary Efficacy Variable at Each Study Visit (ITT Analysis Set)

Default summary statistics per treatment group for the primary efficacy variable (Plasma concentration of Coenzyme Q10) at each study visit will be presented for the ITT analysis set.

This table will be replied on the PP analysis set.

Table 14. Plasma concentration of coenzyme Q10 by gender (ITT Analysis Set)

Default summary statistics per gender for the primary efficacy variable (Plasma concentration of Coenzyme Q10) at each study visit will be presented for the ITT analysis set.

This table will be replied on the PP analysis set.

Table 15. Change versus baseline by Treatment (ITT Analysis Set)

Default summary statistics per treatment group for the change versus baseline at each study visit will be presented for the ITT analysis set.

This table will be replied on the PP analysis set.

Table 16. Pharmacokinetic Parameters by Treatment (ITT Analysis Set)

Default summary statistics per treatment group for each pharmacokinetic parameter will be presented for the ITT analysis set.

This table will be replied on the PP analysis set.

Table 17. Confidence Interval and Results of T-test for Primary Efficacy Variable (ITT Analysis Set)

Confidence interval at 95% will be presented for the means of the pharmacokinetics parameters in the two groups in the ITT analysis set. The table also contains the result of the Student t-test detecting the differences between the two groups.

This table will be replied on the PP analysis set.

A Primary efficacy variable will be presented in subject data listings as follows:

Listing 16. Listing of Primary Efficacy Variable

A listing of the values for the primary efficacy variable (Plasma concentration of Coenzyme Q10) as used in the primary analysis, sorted by screening number and within subjects by time point will be presented.

Listing 17. Listing of Pharmacokinetic parameters

A listing of the values for the pharmacokinetic parameters as used in the primary analysis, sorted by screening number will be presented.

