	Mean (SD)	X.XXX (XX.XX)	X.XXX (XX.XX)	X.XXX (XX.XX)
	95% CI	XX.X/XX.X	XX.X/XX.X	XX.X/XX.X
	CV (%)	XX.XX	XX.XX	XX.XX
	Median	X.XXX	X.XXX	X.XXX
	Interquartile			
	Range	XX.X	XX.X	XX.X
	Min/Max	XX.XX/XX.XX	XX.XX/XX.XX	XX.XX/XX.XX

N: Number of subjects in specified treatment group

n: Number of subjects with data available

SD = Standard deviation

CV = Coefficient of Variation

RUN: DDMMYYYY HH:MM <1MED > Page X of Y

Table 17. Confidence Interval and Results of T-test for Primary Efficacy Variable (ITT Analysis Set)

Parameter	Mean	95% Confidence Interval		Difference between the means of the two groups	P-value
		Lower Limit	Upper Limit		
AUC_t	X.XX	X.XX	X.XX	X.XX	X.XXXX
C_max	X.XX	X.XX	X.XX	X.XX	X.XXXX
T_max	X.XX	X.XX	X.XX	X.XX	X.XXXX
t_(1/2)	X.XX	X.XX	X.XX	X.XX	X.XXXX

Notes:

P-values are referred to a Student t-test comparing means of the two groups. A p-value less than 0.05 indicates a statistically significant difference.

RUN: DDMMYYYY HH:MM <1MED > Page X of Y

	Form	Form No.	1M-DMST-011-01-A1
	Statistical Analysis Plan	Page	Page 47 of 69
		Effective Date	07/05/2018

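### The SAP attaches an uncorrected p < 0.05 significance rule to four unranked OD–BID tests that the protocol does not plan; if the two regimens do not differ at all, the chance of at least one significant result is roughly 9–19%

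*SAP*

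**What the plan says.** The primary objective is to "evaluate the best dosage between 100mg once daily or 100mg twice daily" (SAP 5.2.1; Protocol 7.1 is equivalent). Protocol 12.7 says "The primary variables are the pharmacokinetic properties" and lists AUC, Cmax, Tmax and half-life without ranking them.

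On inference the two documents differ:

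- **Protocol 12.1 and 12.6:** descriptive statistics and 90% confidence intervals; "no hypotheses are pre-specified". Protocol 12.1 also asks that additional analyses be explained in the SAP.
- **SAP 5.2.1:** 95% intervals for the group means, and then "A Student t-test for unpaired data will be performed in order to detect differences between the two groups in the pharmacokinetics parameters".
- **SAP Table 17:** one p-value for each of the four parameters, with the note "A p-value less than 0.05 indicates a statistically significant difference". The table is repeated in the per-protocol (PP) set, which the SAP ranks as supportive.
- **SAP 4.8, on multiple testing:** "Not applicable in this study".
- **SAP 6:** reports no departure from the protocol's analysis.

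The SAP is also inconsistent about what is primary. For Table 13 it writes "Default summary statistics per treatment group for the primary efficacy variable (Plasma concentration of Coenzyme Q10) at each study visit will be presented", but Table 17, whose title refers to the same primary efficacy variable, tests the four derived parameters and not the concentration.

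**The concern.** Declaring multiplicity inapplicable is fair for the protocol's descriptive plan. It no longer fits once a table of four tests carries a fixed significance threshold. Nothing ranks the parameters or says how four results combine, so a lone p < 0.05 on Tmax or half-life would have the same standing in Table 17 as one on AUC_t. Yet the objective concerns the plasma level reached, which AUC and Cmax describe and the other two do not.

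At stake is what the report may say. A reader of Table 17 would take 5% as the chance of a spurious significant result, when that figure applies to each row and not to the table.

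**Working it through.** **What there is to reproduce.** Neither document states a family-wise error, power, SD or correlation. The only stated figure is the 0.05 threshold per test.

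**Inputs from the documents.** Four tests (SAP 5.2.1, Table 17); 12 subjects per arm (SAP 2.5), so 22 degrees of freedom; multidose samples on days 0, 7, 14 and 28 (SAP 4.3); expected levels of about 2.5 (OD) and 3.5 µg/ml (BID) (Protocol 6.1). Sidedness is not stated; two-sided is assumed, because the test looks for differences. The PP repeat is not counted.

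**Half-life formula (SAP 5.2.1).** The elimination constant is clearance over volume: (dose/AUC) ÷ (dose/C0) = C0/AUC. Dose cancels, so t½ = ln 2 × AUC/C0, with C0 the Visit 2 value in the multidose phase.

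**Step 1: no true difference, independent tests.** 1 − 0.95⁴ = 18.5%. The bound under any dependence is 4 × 0.05 = 20%.

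**Step 2: no true difference, four equally correlated tests, 12 per arm (simulated).**

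| Pairwise correlation | At least one p < 0.05 |
|---|---|
| 0 | 18.7% |
| 0.3 | 17.4% |
| 0.5 | 15.9% |
| 0.7 | 13.3% |
| 0.8 | 11.7% |
| 0.9 | 9.6% |

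A separate run of the same calculation gave 18.6% at correlation 0 and 9.4% at 0.9. Hence roughly 9–19%.

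**Step 3: no true difference, parameters derived as the SAP prescribes.** Log-normal concentrations at the four visits were simulated with assumed CV 30–50%, between-visit correlation 0.3–0.8 and three assumed mean profiles (baseline 0.8 µg/ml, staying flat or rising to 2.5), with 40,000 trials per scenario. Each single test rejects in 4.4–5.4% of trials; at least one rejects in 14.4–15.9%. AUC and Cmax correlate at 0.86–0.98. Tmax and half-life are only weakly related to those two, so the family behaves like about three independent tests: 1 − 0.95³ = 14.3%. Other assumed variability (subject SD 0.2–0.3, within-subject SD 0.1–0.3, rise SD 30%) gives 13.0–13.9%, and further runs on similar assumptions 12.5–14.9%. Hence about 12–16%. If nearly every subject peaked at the same visit, Tmax would hardly count as a test, and about two independent tests would remain: 1 − 0.95² = 9.8%.

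**Step 4: the protocol's expected levels.** Take an illustrative OD mean profile of 0.8, 1.8, 2.2, 2.5 and scale its rise by 2.7/1.7 to reach 3.5 for BID: 0.8, 2.388, 3.024, 3.5.

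- AUC, OD: 9.1 + 14.0 + 32.9 = 56.0 µg/ml × day.
- AUC, BID: 11.2 + 18.9 + 45.7 = 75.8 µg/ml × day.
- t½ by the SAP formula: 0.693 × 56.0/0.8 = 48.5 days against 0.693 × 75.8/0.8 = 65.7 days.

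AUC, Cmax and the SAP's half-life all truly differ. Half-life differs only because AUC does, relative to the same baseline. The peak is on day 28 in both arms, so Tmax is the one parameter left for a false positive. In simulations of 2.5 against 3.5 under the variability assumptions above, Tmax was significant in 1.6–5.9% of trials, at or below about the nominal level.

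**The case against.** The strongest reply is that the study is exploratory. Protocol 12.6 pre-specifies no hypotheses, SAP 2.5 speaks of exploratory purposes, and neither document promises family-wise control. SAP 5.2.1 even says "Area under the curve, maximum concentration in the plasma, time of maximum concentration and terminal half-life will be presented descriptively on the original scale". All four rows of Table 17 are printed, so nothing is selected out of sight.

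Much of this stands. No formal alpha control is owed, and the point is one of reporting. But the descriptive statement does not expressly cover the p-values, and the SAP labels its gender analysis explorative while giving the OD–BID tests no such label. The Table 17 footnote then turns each p-value into a finding of significance.

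Two stronger readings are tempting, and the documents support neither. A reader might infer that the false-positive risk is inflated whatever the truth; it is inflated only if OD and BID are alike on every parameter, and the protocol expects otherwise. A reader might also infer that p < 0.05 settles the dosage. No section says so: the objective is a plasma level, and Protocol 12.7 attaches thresholds to AUC, Cmax and Tmax.

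**Conclusion.** The point holds as a reporting defect of moderate weight. The SAP adds four significance tests to a descriptive protocol, gives them a 0.05 rule without any multiplicity statement, and records no change.

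Its size is conditional. With no OD–BID difference on any parameter, the chance of at least one significant row is roughly 9–19% for pairwise correlations from 0.9 down to 0, and about 12–16% with the SAP's formulas. Both ranges rest on assumed variability and correlation. Under the protocol's own expectation the false-positive risk lies essentially with Tmax, at about 5%.

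It might seem to follow that one deciding parameter must be named. It does not: the protocol's list has no order and the study is not powered. In simulations of 2.5 against 3.5 µg/ml, AUC_t reached significance in only about 38–70% of trials, so making it the gatekeeper has a real price.

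**What to change.** Before database lock:

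1. Delete the 0.05 significance footnote from Table 17.
2. In SAP 4.8 and Table 17, state that the four p-values, in both the ITT and PP sets, are exploratory and unadjusted and support no claim of a significant difference between dosages.
3. Report each OD–BID difference with its confidence interval; Table 17 currently provides intervals for the group means and only a point value for the difference. Use 90% as in the protocol, or record the move to 95% in SAP 6.
4. List the added t-tests in SAP 6.

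Using one definition of the primary efficacy variable throughout would remove the labelling conflict at the same time. Naming AUC_t as the single deciding contrast, tested at 5%, is an option open to the sponsor and not a required correction.

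The cost is SAP wording and one added interval in Table 17; no new data, subjects or procedures are needed. The downside is that no single p < 0.05 can then be reported as a significant dosage difference.

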5.2.2 Analysis of Secondary Variables

	Form	Form No.	1M-DMST-011-01-A1
	Statistical Analysis Plan	Page	Page 24 of 69
		Effective Date	07/05/2018

Secondary objectives of this study are:

- To evaluate the safety and tolerability COQUN ORAL FORMULATION following single dose of 100mg
- To evaluate the safety and tolerability of COQUN ORAL FORMULATION during the 1 month daily dose

The secondary variables are the ones regarding safety which will be monitored through:

- Vital signs
- Adverse events

Special interest will be paid on symptoms and signs like mild insomnia, elevated levels of liver enzymes, rash, nausea, upper abdominal pain, dizziness, sensitivity to light, irritability, headache, heartburn, and fatigue.

Analysis of safety will be performed on the safety analysis set.

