12 BIOSTATISTICAL METHODS

12.1 General

Due to the explorative aim of the study, descriptive statistics and confidence intervals at 90% level will be provided.

In particular, continuous variables will be presented as arithmetic mean values \pm standard deviation (SD) and median values with interquartile range; geometric means will be provided as well; for categorical variables absolute and percentage frequencies will be provided.

All data collected during the study visits and up to V5 (EOS) will be presented for the two groups.

Any major deviations from this plan, the reasons for such deviations, and all alternative or additional statistical analyses that may be performed will be explained in the Statistical Analysis Plan (SAP), which will give a detailed technical description of all statistical analyses. All deviations and/or alterations will be summarized in the Clinical Study Report (CTR).

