12.8 Analysis of Secondary Variables

The secondary variables are the ones regarding safety which will be monitored through vital signs, physical exams, ECGs, clinical laboratory tests and adverse events, as follows:

- Following a single oral dose of 100mg COQUN ORAL FORMULATION
- in 1 month period of daily oral intake of 100mg OD or BID COQUN ORAL FORMULATION

Symptoms and signs like mild insomnia, elevated levels of liver enzymes, rash, nausea, upper abdominal pain, dizziness, sensitivity to light, irritability, headache, heartburn, and fatigue will be closely monitored.

At each time point and for each group, descriptive statistics will be provided. See section **12.9** for details.

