12.9.2 Clinical Laboratory

Clinical laboratory data will be presented on an individual basis and will be marked according to the normal ranges provided by the selected central laboratory and corresponding sponsor guidelines, respectively. Descriptive summary statistics will be presented for each variable. In addition, the number of subjects with values outside the normal range and extended normal ranges will be presented.

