5.3 Pharmacokinetic (PK)/ Pharmacodynamic (PD)

Pharmacokinetic properties evaluated for this study are the following:

- Area under the curve (AUC_t)
- Maximum concentration in the plasma (C_{max})
- Time taken to reach the maximum concentration (T_{max})
- Elimination half-life ($t_{1/2}$)

The detailed description of the analysis of pharmacokinetic variables is provided in section 5.2.1 Primary efficacy analysis.

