6. CHANGES TO THE ANALYSIS AS LAID DOWN IN THE PROTOCOL AND AMENDMENTS

No changes to the analysis as laid down in the protocol were made.

1MED Regulatory & Clinical Development	Form	Form No.	1M-DMST-011-01-A1
	Statistical Analysis Plan	Page	Page 31 of 69
		Effective Date	07/05/2018

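### The SAP plans none of the three laboratory safety outputs that Protocol 12.9.2 specifies, yet declares that no changes were made

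*SAP*

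**What the plan says.** Protocol 7.2 and 12.8 define the secondary variables as safety variables "monitored through vital signs, physical exams, ECGs, clinical laboratory tests and adverse events". For all of them 12.8 promises: "At each time point and for each group, descriptive statistics will be provided". It then refers to 12.9 for details.

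Protocol 12.9.2 sets out the laboratory outputs:

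- First: "Clinical laboratory data will be presented on an individual basis and will be marked according to the normal ranges".
- Second, descriptive summaries for each laboratory variable.
- Third: "the number of subjects with values outside the normal range and extended normal ranges will be presented".

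SAP 5.2.2 covers the same secondary variables, with the lead-in "The secondary variables are the ones regarding safety which will be monitored through", but the list that follows has two entries, vital signs and adverse events, and its two subsections treat exactly those. SAP 6 states: "No changes to the analysis as laid down in the protocol were made". Protocol 12.1 says that "Any major deviations from this plan, the reasons for such deviations" are to be explained in the SAP, which is also meant to describe every analysis in technical detail.

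**The concern.** Safety and tolerability, after the single dose and over the month of daily dosing, are the study's two secondary objectives. Laboratory data are one of the five kinds of evidence that the protocol assigns to them. A programmer working from the SAP alone would produce no laboratory output. A reader of SAP 6 would take that to be what the protocol asked for, and could not tell an oversight from a decision. What is at stake is the completeness of the secondary safety reporting. The primary pharmacokinetic analysis is not affected.

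**Working it through.** No formula applies and the plan gives no figure to reproduce. The check sets the two documents side by side and counts.

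**1. Safety domains in Protocol 12.8 against SAP outputs**

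| Domain | Planned in the SAP |
|---|---|
| Adverse events | Tables 18–23, Listings 18–21: 6 + 4 = 10 |
| Vital signs | Table 24, Listings 22–23: 1 + 2 = 3 (plus line graphs) |
| Physical examination | Table 9, Listing 10, Visit 1 only (in SAP 5.1.5, not 5.2.2) |
| Clinical laboratory tests | None |
| ECG | None |

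SAP 5.2.2 therefore plans 10 + 3 = 13 tables and listings, none of them for laboratory data.

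**2. Elsewhere in the SAP.** The output lists in SAP 8.1 hold 28 + 25 + 7 = 60 titles, none for safety laboratory data. Those lists are not exhaustive, since the vital-sign graphs and the per-protocol repeats appear only in the text. But the text adds no laboratory output either:

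- SAP 5.2.3 covers single-dose pharmacokinetics.
- SAP 5.3 opens with "Pharmacokinetic properties evaluated for this study are the following" and lists four pharmacokinetic parameters.
- Table 7 records whether blood was taken at each visit, not what was found.

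Removed pages do not explain the gap. The numbered lists run without a break, and the SAP contents page shows only adverse events and vital signs under 5.2.2.

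**3. Laboratory outputs in Protocol 12.9.2**

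| Output | In the SAP |
|---|---|
| Individual data marked against normal ranges | No |
| Descriptive statistics per variable (by time point and group under 12.8) | No |
| Number of subjects outside normal and extended normal ranges | No |

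The result is 0 of 3. The data are scheduled: Protocol 10.6.9 places laboratory assessments at V1 and on Days 0, 7, 14 and 28, and names a haematology panel.

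**4. What reaches the adverse event tables.** Under Protocol 11.1.1, clinically significant changes from baseline are adverse events. Post-screening values beyond the alert limits must also be recorded as such, with exceptions that include a parameter already beyond the limit at screening. Under 10.6.9, an out-of-range value may be marked as not clinically significant. A value that is outside the normal range, so marked, and within the alert limits need not become an adverse event, yet the third output in 12.9.2 would count it. For the values that do become adverse events, the tables show the event and not the measurement.

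**5. Neighbouring inconsistencies, at lower confidence**

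- *ECG.* Named in Protocol 12.8 and scheduled at screening and end of study in 10.6.7. Absent from the synopsis safety row, the flow chart, the V2–V5 visit lists (10.5.2, 10.5.3) and all of 12.9.
- *Physical examination.* A secondary variable in 12.8, and marked at V2–V5 in the flow chart. Absent from the V2–V5 visit lists, and confined to Visit 1 in SAP 5.1.5.
- *Serum chemistry.* Included in the synopsis and given a tube in 10.6.9. Protocol 10.7 and 12.9.1 mention haematology only. Apart from a glucose tube no chemistry panel is listed, although liver enzymes are to be watched closely and SAP Tables 20–21 carry a row for them.

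**The case against.** The best defence has three parts. Important laboratory abnormalities become adverse events and so reach the tables. The study is exploratory, with 24 subjects and no power calculation. And Protocol 12.1 asks only for major deviations to be explained, while nothing in the SAP withdraws 12.9.2.

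The first part stands in part: the abnormalities that matter most should appear as adverse events, but the lesser out-of-range values need not and the measurements do not. The second sets a ceiling on the importance of the point. It does not excuse the gap, because the missing outputs are themselves purely descriptive. On the third, whether the omission is major is a judgement. The statement in SAP 6 carries no such qualifier, so it is inaccurate either way.

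A reader might infer more than the documents support:

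- *That the laboratory results were deliberately dropped, or will certainly be missing from the report.* The SAP does not say so. What can be shown is that it does not implement 12.9.2.
- *That the ECG omission is equally firm.* Protocol 12.8 gives one general sentence and defers to 12.9, which specifies no ECG output. No ECG listing is promised anywhere.
- *That the silence of SAP 5.3 on pharmacodynamics is a further departure.* Protocol section 12 plans no pharmacodynamic analysis. The silence shows only that haematology gets no output by that route.
- *That liver enzymes are not measured, or that there is a hepatic or cardiac risk.* The documents are unclear about the panel and support neither conclusion.

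**Conclusion.** The point holds, with high confidence, for laboratory data: 0 of the 3 outputs specified in Protocol 12.9.2 are planned, and SAP 6 is wrong to report no change. It does not depend on settling the chemistry question, because 10.6.9 already names a haematology panel. It assumes that the SAP's sections and output lists are the whole plan, which their unbroken numbering supports. It should be corrected, but it concerns descriptive secondary outputs in a small exploratory study. The ECG, physical examination and chemistry items are matters to reconcile, mainly within the protocol, and do not carry the same weight.

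**What to change.** **SAP 5.2.2.** Add three laboratory outputs on the Safety set: a by-subject listing flagged against normal ranges, descriptive statistics for each variable by visit and group, and counts of subjects outside the normal and extended normal ranges. Define the extended ranges first. Protocol 12.9.2 points only to the central laboratory and to sponsor guidelines, so the last output cannot yet be programmed. If any of the three is dropped on purpose, declare and justify that instead.

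**SAP 6.** Correct the statement in either case, before the SAP is signed. The SAP introduction requires signature before hard lock of the database.

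**Reconciliation**

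- ECG: add a descriptive summary of the recorded interpretation, or state that none is planned, and align Protocol 10.6.7 with the flow chart and visit lists.
- Physical examination: reconcile Protocol 12.8, the flow chart, the V2–V5 visit lists and SAP 5.1.5.
- Chemistry: reconcile the synopsis, 10.6.9, 10.7 and 12.9.1 on whether serum chemistry belongs to the safety panel and whether liver enzymes are assayed.

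**Cost.** A few shells, some programming, a corrected SAP 6 and a protocol clarification. This rests on the laboratory values being captured. Protocol 10.6.9 mentions a laboratory CRF page and 14.3 requires protocol-procedure data in the CRF, but the SAP names no laboratory CRF field, so capture should be confirmed first.
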